4.5.2. Adverse Events

All Adverse Events (AEs) will be coded using the MedDRA coding system (version 23.0 or later) and displayed in tables and data listings using SOC and PT.

Summaries of AEs will be performed for those events that are considered treatment-emergent, where a treatment-emergent is defined as any AE with onset during or after the first administration of patisiran in this study through 28 days after the last dose of patisiran. In addition, any event that was present at baseline but worsened in intensity or was subsequently considered drug-related by the Investigator through the end of the study will be considered treatment-emergent.

An AE related to study drug is defined as an AE identified by the investigator having a reasonable possibility that the event may have been caused by the study drug. An AE without an assessment by the investigator as to whether there was or was not a reasonable possibility that the AE may have been caused by the study drug, will be considered as an AE related to study drug.

An AE with a missing severity will be considered as severe.

AEs will be tabulated by the frequency and percentage of patients reporting a given AE. A patient contributes only once to the count for a given AE (overall, by SOC, by PT).

An overall summary of AEs will include the number and percentage of patients with at least one AE, AE assessed by investigator as related to treatment, severe AE, severe AE related to treatment, serious AE (SAE), SAE related to treatment, AE leading to study drug interruption, study drug related AE leading to study drug interruption, AE leading to treatment discontinuation, study drug related AE leading to treatment discontinuation, AE leading to study withdrawal, study drug related AE leading to study withdrawal, and deaths.

Tabulations by SOC and PT will be produced for the following:

- all AEs,
- severe AEs,
- SAEs,
- AEs related to study drug,
- AEs leading to study drug interruption,
- AEs leading to treatment discontinuation,
- AEs leading to study withdrawal,
- AEs related to pre-medication,
- AEs over time.

AEs, AEs related to study drug and SAEs will also be tabulated by PT in decreasing order of frequency.

AEs and AEs related to study drug will be summarized by maximum severity; patients who report multiple occurrences of the same AE (preferred term) will be classified according to the most severe occurrence.

AEs mapping to the Drug Related Hepatic Disorder standardized MedDRA query (SMQ) will be summarized by SOC and PT. Other SMQs or AE groupings may be evaluated.

By-patient data listings will be provided separately for each of the following:

- AEs (including both treatment emergent and non-treatment emergent AEs),
- all patient deaths (regardless of whether or not it was associated with an AE),
- SAEs,
- AEs leading to treatment discontinuation or study withdrawal,
- AEs related to premedication.

IRR signs and symptoms will be summarized by SOC and PT. The incidence and frequency of IRR signs and symptoms over time will also be summarized by SOC and PT.

A separate listing will also be provided for IRR signs and symptoms.

Additional AE considerations regarding COVID-19 are detailed in Section 4.7.3.

4.5.3. AEs of Clinical Interest (AECI)

The following events will be considered as AECI for this study: ALT or AST elevations $> 3 \times \text{ULN}$, or potential or confirmed events of liver transplant rejections. The number and percentage of patients and the number of events will be summarized for events of ALT or AST elevations $> 3 \times \text{ULN}$ and potential or confirmed events of liver transplant rejections.

Separate listings will be provided for AECIs as collected in Supplemental AE of Clinical Interest (AECI) – Liver Function Test Elevations form and Liver Allograft Status form.

4.5.4. Laboratory Data

Laboratory data include hematology, serum chemistry, coagulation, liver function tests and pregnancy tests. Clinical laboratory values will be expressed in SI units.

Summary data for each laboratory parameter will be presented for each continuous clinical laboratory parameter (including hematology, serum chemistry, and liver function tests). Descriptive statistics will be presented for the actual values, change from baseline, and percent change from baseline by scheduled visit. For each continuous laboratory parameter, results will be categorized as low, normal, or high based on the laboratory normal ranges. Shift tables will be employed to summarize the baseline category versus the “worst” post-baseline category for selected parameters.

Coagulation parameters (collected at screening) will be descriptively summarized.

A listing will be produced for all patients with abnormal liver function tests defined as an ALT $> 3 \times \text{ULN}$, AST $> 3 \times \text{ULN}$, and/or total bilirubin $> 2 \times \text{ULN}$ at any time point.

A table will be produced to summarize the number and percentage of patients in each of the below categories at any post-baseline time point.

- ALT >1 & ≤3, >3 & ≤5, >5 & ≤10, >10 & ≤20, >20 ×ULN,
- AST >1 & ≤3, >3 & ≤5, >5 & ≤10, >10 & ≤20, >20 ×ULN,
- ALT or AST >1 & ≤3, >3 & ≤5, >5 & ≤10, >10 & ≤20, >20 ×ULN,
- ALP >1.5 ×ULN,
- Total Bilirubin >1.5 & ≤2, >2 & ≤3, >3 & ≤5 and >5 ×ULN,
- Total Bilirubin >2 ×ULN concurrent with ALT or AST >3 ×ULN.

The peak total bilirubin (at any time post-baseline) will be plotted against the peak AST or ALT level at any time post-baseline.

Laboratory test results will be graded according to the NCI CTCAE Version 5.0 or above, where applicable. A shift summary of baseline to maximum post-baseline CTCAE grade may be presented, as appropriate.

The eGFR (mL/min/1.73 m²) will be categorized as follows: ≥90; 60-89; 45-59; 30-44; 15-29 and <15. A shift summary of baseline to worst post-baseline eGFR category will be presented.

All laboratory data will be included in by-patient data listings. Laboratory values outside of the normal ranges will be identified in the listings.

4.5.5. Vital Signs and Physical Examination

The observed values and changes from baseline for weight and vital signs (blood pressure, pulse rate, body temperature, and respiration rate) will be summarized by scheduled visit. The frequency and percentage of patients with potentially clinically significant vital signs will also be presented.

Vital sign measurements will be included in a by-patient data listing.

4.5.6. Premedications

Premedications will be coded using the WHO Drug Dictionary (September 2018 or later). Results will be tabulated by anatomic therapeutic class (ATC) and PT. Premedication data will be presented in a by-patient data listing.

4.5.7. Concomitant Medications

Concomitant medications will be defined as those medications that were initiated after first patisiran administration or those that were ongoing at the time of the first patisiran administration. For medications with partial start or stop dates: the first day/month of the specified month/year will be imputed for start date, and the last day/month of the specified month/year will be imputed for stop date. For medications with a completely missing start date, the medications will be considered as started prior to the first dose of study drug; medications will be classified as prior, concomitant or both depending on the medication stop dates. For medications with a completely missing stop date, the end of study date will be used.

Concomitant medications will be tabulated by ATC and PT; a patient will only be counted once for each ATC or PT if they have multiple medications with the same ATC or PT.

Concomitant medications will be included in a by-patient data listing.

4.5.8. Hospitalizations/Healthcare Encounters and Outpatient Procedures

Hospitalizations/healthcare encounters and outpatient procedures data will be included in by-patient listings.

4.6. Anti-Drug Antibody (ADA)

Serum blood samples will be collected to evaluate antidrug antibodies. Anti-PEG₂₀₀₀-C-DMG antibody measurements will be taken predose on scheduled infusion days.

Anti-drug antibody data including the confirmed ADA positive results flag will be included in a by-patient data listing.

4.7. COVID-19 Global Pandemic

Additional data were collected to characterize the impact of the COVID-19 pandemic on general study conduct, disposition, and subsequently, additional analyses and summaries will be provided in acknowledgement of multiple regulatory guidances (FDA Guidance on Conduct of Clinical Trials of Medical Products during COVID-19 Pandemic: Guidance for Industry, Investigators, and Institutional Review Boards, US Food and Drug Administration, July 2020; Guidance on the Management of Clinical Trials during the COVID-19 (Coronavirus) Pandemic, European Medicines Agency, April 2020; Points to consider on implications of Coronavirus disease (COVID-19) on methodological aspects of ongoing clinical trials, European Medicines Agency, June 2020; Statistical Considerations for Clinical Trials During the COVID-19 Public Health Emergency, US Food and Drug Administration, June 2020).

4.7.1. General Impact

Patients who discontinue treatment or discontinue study participation due to COVID-19 will be included in patient disposition summaries as described in Section 4.1.

Impact on study participation due to COVID-19, including visit completion, visit location changes, and study drug dosing changes, will be summarized overall on the patient level with both continuous and categorical descriptives, and overall and by visit on the event level with categorical descriptives. Patient- and event-level summaries of the impact on study participation due to COVID-19 may also be generated by site and/or region.

Impact on study participation due to COVID-19 will be presented in data listings by patient and by visit within patient.

Protocol deviations due to COVID-19 will be presented in a patient data listing as described in Section 2.2.

4.7.2. Impact on Efficacy Endpoints

The Per Protocol Analysis Set as defined in Section 2.1 will be used for secondary and exploratory efficacy endpoints analyses.

Secondary and exploratory efficacy assessments on or after the onset of a serious COVID-19 AE for a patient may be censored (see Section 3.9).

Summaries of missing efficacy data due to COVID-19 pandemic will be included in a missing efficacy data summary table as described in Section 3.10.

4.7.3. Impact on Adverse Events

An overall summary of AEs mapping to a COVID-19 custom query will include the number and percentage of patients with at least one AE, AE assessed by the Investigator as related to treatment, severe AE, severe AE related to treatment, SAE, any SAE related to treatment, AE leading to study drug interruption, study drug related AE leading to study drug interruption, AE leading to treatment discontinuation, study drug related AE leading to treatment discontinuation, AE leading to study withdrawal, study drug related AE leading to study withdrawal, and deaths. AEs mapping to the COVID-19 custom query will be summarized by HLT and PT. Due to the evolving nature of COVID-19 related MedDRA terminology, the COVID-19 custom query will be based on the latest information available at the specified analysis timepoint.

An overall summary of AEs by pandemic phase (see Section 7.2) will include the number and percentage of patients with at least one AE, AE assessed by the Investigator as related to treatment, severe AE, severe AE related to treatment, SAE, any SAE related to treatment, AE leading to study drug interruption, study drug related AE leading to study drug interruption, AE leading to treatment discontinuation, study drug related AE leading to treatment discontinuation, AE leading to study withdrawal, study drug related AE leading to study withdrawal, and deaths. AEs and SAEs will be summarized by pandemic phase, SOC, and PT.

AEs mapping to the COVID-19 custom query will be presented in a data listing.

Events will be considered during the pandemic if the event occurs on or after confirmed case of COVID-19 based on the country where the study site is located, described in Section 7.2.

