1.2. Study Design

1.2.1. Synopsis of Study Design

Study 008 is a global Phase 3b open-label study designed to evaluate the safety, efficacy, and PK of patisiran in patients with hATTR amyloidosis with disease progression after liver transplant. All eligible patients will be administered open-label patisiran.

The open-label design is supported by previous studies, including a pivotal Phase 3 double-blind, placebo-controlled study (ALN-TTR02-004; hereinafter referred to as the APOLLO study). The clinical benefits seen in the APOLLO study were observed in association with an 80% reduction of TTR with patisiran within 10 to 14 days after a single dose, which was maintained over the duration of the 18-month study compared to no change with placebo. The primary efficacy endpoint in the current study, TTR reduction, is an objective measurement and not susceptible to bias of clinical study center staff or study patients and therefore does not require a blinded placebo group for accurate interpretation.

Consented eligible patients enrolled in this study will receive 0.3 mg/kg patisiran IV once every 3 weeks for 12 months. Dosing is based on actual body weight. For patients weighing 100 kg or more, patisiran will be administered at a total dose of 30 mg IV once every 3 weeks. Eligibility for this study will be confirmed before administration of the first dose on Day 1.

Safety will be assessed throughout the study. Patients will return to the clinical site for safety evaluations at Week 12, Month 6, and Month 12. Patients will be continually assessed throughout the study for adverse events (AEs). Unscheduled visits for study assessments may occur if deemed necessary by the study personnel.

Efficacy assessments will be performed at baseline, 6 and 12 months.

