7.2. Pandemic Phase Start Dates by Country

Table 1 Pandemic Phase Start Dates by Country

Country	Date of 1 st Confirmed Case
France	2020-01-24
Germany	2020-01-28
Italy	2020-01-29
Portugal	2020-03-02
Spain	2020-01-31
Sweden	2020-01-31
United Kingdom	2020-01-31

As reported by the World Health Organization and the Taiwan Centers for Disease Control.

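### The adverse event summary by pandemic phase gives crude patient percentages without time at risk per phase, so the percentages partly reflect length of observation

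*SAP*

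**What the plan says.** SAP 4.7.3 plans two displays by phase. The first is an overview: "An overall summary of AEs by pandemic phase (see Section 7.2) will include the number and percentage of patients with at least one AE", followed by the related, severe, serious, interruption, discontinuation, withdrawal and death categories. The second is more detailed: "AEs and SAEs will be summarized by pandemic phase, SOC, and PT".

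The boundary is a calendar date tied to the site's country: "Events will be considered during the pandemic if the event occurs on or after confirmed case of COVID-19 based on the country". The dates are in SAP 7.2, "Pandemic Phase Start Dates by Country", and run from 24 January 2020 (France) to 2 March 2020 (Portugal).

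The general counting rules are in SAP 4.5.2: "AEs will be tabulated by the frequency and percentage of patients reporting a given AE", and "A patient contributes only once to the count for a given AE (overall, by SOC, by PT". An AE is treatment-emergent with "onset during or after the first administration of patisiran in this study through 28 days after the last dose of patisiran". Planned treatment is "0.3 mg/kg patisiran IV once every 3 weeks for 12 months" (SAP 1.2.1).

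SAP 4.5.1 defines duration of exposure once, over the whole study. SAP 4.5 names the Safety Analysis Set for safety analyses in general. Neither document provides patient-time by phase, an exposure-adjusted rate, or a denominator restricted to patients at risk in a phase. Under SAP 3.2, everything other than the primary endpoint is descriptive.

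**The concern.** The percentage of patients with at least one event rises with the time they are watched, because each patient is counted once. Cutting at a fixed date gives each patient a share of follow-up in each phase that depends on when that patient was first dosed and in which country. A patient who finished before the date has no time in the pandemic phase; one first dosed after it has no time in the earlier phase.

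Two columns of percentages from unequal follow-up invite a reader to see a rise or fall in events during the pandemic. With about 20 patients, a few who have little time in one phase can move the figures visibly. At stake is the interpretation of one supportive safety display.

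**Working it through.** **Figures the plan gives.** The SAP states no figure for this table. The only planned number that bears on it is the sample size: 16 / (1 − 0.20) = 20 patients (SAP 3.1), which reproduces. It is used below as the largest likely denominator.

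**Step 1: can the boundary cut a patient's AE window?** Protocol Table 1 schedules the last dose at Week 54. Adding 28 days gives 58 weeks = 406 days, and 406 / 30.4375 = 13.3 months. A patient at a French site straddles 24 January 2020 if first dosed from 15 December 2018 to 23 January 2020. A patient at a Portuguese site straddles 2 March 2020 if first dosed from 22 January 2019 to 1 March 2020. The protocol is dated 7 October 2018, so such first-dose dates are possible, but actual enrolment dates are not given.

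**Step 2: how unequal can the split be?** Assumed first-dose dates, French boundary:

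| First dose (assumed) | Months before | Months during |
|---|---|---|
| 1 Mar 2019 | 10.8 | 2.5 |
| 1 Jun 2019 | 7.8 | 5.6 |
| 1 Sep 2019 | 4.8 | 8.6 |
| 1 Dec 2019 | 1.8 | 11.6 |

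**Step 3: what do crude percentages show when nothing changes?** Assume one constant rate λ in both phases. The expected percentage with at least one event in m months is 1 − exp(−λm). For a 12-month risk c, λ = −ln(1 − c)/12, so the percentage equals 1 − (1 − c)^(m/12).

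- c = 25%, split 9/3 months: 1 − 0.75^0.75 = 19.4%; 1 − 0.75^0.25 = 6.9%.
- c = 50%, split 9/3 months: 1 − 0.50^0.75 = 40.5%; 1 − 0.50^0.25 = 15.9%.
- c = 25%, split 6/6 months: 1 − 0.75^0.5 = 13.4% in both phases.

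Over the full 13.3-month window, with 10.3 months before and 3.0 during:

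| True rate per 100 patient-months, both phases | Before | During |
|---|---|---|
| 2 | 18.7% | 5.8% |
| 5 | 40.4% | 13.9% |
| 10 | 64.4% | 25.9% |
| 30 | 95.5% | 59.3% |

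Reversing the split reverses the sign. An equal split (6.7/6.7 months) gives no difference at any rate.

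**Step 4: does the denominator matter?** Assume 20 patients at the French boundary: 6 first dosed on 1 December 2018, 7 on 1 March 2019 and 7 on 1 June 2019, at 10 events per 100 patient-months. The first 6 finish before the boundary, leaving 14 at risk in the pandemic phase. Time at risk is 210 versus 57 patient-months. Expected patients with an event are 12.83 before and 4.55 during.

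- Denominator 20 in both phases: 12.83/20 = 64.2% versus 4.55/20 = 22.7%.
- At-risk denominator during the pandemic: 4.55/14 = 32.5%.

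The denominator alone moves the pandemic figure by about 10 points, and the gap remains. The expected rate is 10 per 100 patient-months in both phases, as assumed.

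**Step 5: how precise would a rate be?** In that cohort the pandemic phase expects 57 × 0.10 = 5.7 events. Treating the count as Poisson, the relative standard error is about 1/√5.7 = 42%.

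**The case against.** The strongest reply is that the SAP mis-specifies nothing. It plans a side-by-side summary with no difference, ratio or test between phases; SAP 3.2 makes it descriptive and SAP 3.6 recognises a single hypothesis in the study. That stands: a reader might infer that a formal comparison of phases is planned, and the documents do not support this. The remaining risk is misreading the display.

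Second, the SAP does not say that patients with no time in a phase will be counted in its denominator. Table shells may settle this and are not in the documents. That also stands. The fair statement is that the phase denominator is unspecified, not that a wrong one was chosen.

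Third, SAP 4.7.4 flags pandemic-period records in the AE and exposure listings, and SAP 4.5.2 plans a tabulation of AEs over time. With about 20 patients, time in each phase can be reconstructed by hand. True, but neither output adjusts the phase table or appears beside it.

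Fourth, the table is one display among several. The COVID-19 custom query in the same section addresses pandemic-related events more directly. This limits the importance of the point.

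Fifth, rates do not isolate a pandemic effect. For any patient who straddles the boundary, the earlier phase is also earlier on treatment. A reader might infer that rates would make the phases comparable; they would not. They remove only the part of the difference due to length of observation.

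**Conclusion.** The point holds as a limitation of a descriptive table. As written, the phase percentages mix event frequency with observation time, because a calendar cut across staggered windows of about 13 months gives equal time in both phases only by coincidence. No provision in either document corrects for this.

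Its size and direction in this trial are unknown. The 19.4% versus 6.9% illustration assumes a constant rate, a 25% 12-month risk and a 9/3-month split; the difference could be nil or reversed. It would be wrong to read the resulting 2.8-fold ratio (19.4/6.9) as a property of this study. For frequent events the ratio is smaller: 95.5% versus 59.3% is about 1.6-fold. The primary endpoint and main safety tables are unaffected, so this is an improvement worth making and not a flaw in the trial's conclusions.

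**What to change.** In SAP 4.7.3, for each pandemic phase:

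1. Define the denominator as patients with any treatment-emergent time in that phase, and show that number.
2. Report total patient-months at risk in the phase.
3. Beside the planned counts and percentages, add exposure-adjusted event rates per 100 patient-months at risk in the phase.
4. State that the rates are descriptive, imprecise with about 20 patients, and still confounded by time on treatment, because the pre-pandemic phase always comes first for patients who straddle the boundary.

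The inputs are dosing dates, AE dates and the SAP 7.2 dates, all already available. The cost is a little extra programming; no planned output is lost and no new data are needed.

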4.7.4. Other Impacts

Adverse event, study drug exposure, and efficacy listings will include identification of assessments occurring during the pandemic.

For patients reporting any AEs mapping to the COVID-19 custom query, AEs and prior and concomitant medications will also be presented in separate data listings.

5. CHANGES TO PLANNED ANALYSES

Modifications to planned analysis specifications from the protocol are documented below:

Section	Description	Rationale
Section 2.1	Per Protocol Analysis Set was added.	The Per Protocol Analysis Set was added to support primary analyses of estimating treatment effects of secondary and exploratory efficacy endpoints in patients who did not miss or missed less than or equal to 2 doses of patisiran due to COVID-19.
Section 4.4.1	The Hodges-Lehmann method's estimates of median TTR percent reduction and its 2-sided 95% CI were modified to standard median TTR percent reduction and its 2-sided 95% distribution-free CI, respectively.	The reason of the change is because there is no available SAS procedure in most current SAS version for one-sample Hodges-Lehmann method. Based on simulations, the estimated medians and the 2-sided 95% CIs are similar for the two methods.
Section 3.10.1 Section 4.4.2.1 Section 4.4.2.2 Section 4.4.2.4	The primary analysis for the NIS, Norfolk QOL-DN, R-ODS and mBMI efficacy endpoints was updated to use LOCF to impute missing post-baseline values.	The changes from baseline in NIS, Norfolk QOL-DN and R-ODS assessments between Months 9 and 18 and mBMI assessments between Months 3 and 18 were relatively stable in the patisiran arm of the APOLLO study. Thus, the LOCF method was adopted to account for the potential missingness (including missingness related to COVID-19) in NIS, Norfolk QOL-DN, R-ODS and mBMI efficacy endpoints during this study.
Section 4.4.2.3	The primary analysis for the COMPASS-31 efficacy endpoint was changed to MMRM.	The changes from baseline in COMPASS-31 total score showed improvement from Month 9 to Month 18 in the patisiran arm of the APOLLO study. Thus, the MMRM method was adopted to account for potential missingness (including missingness related to COVID-19) in COMPASS-31 total score, which assumes data are Missing at Random (MAR).

